3. METHODS

Study design

The study is a randomised controlled pilot study that follows the guidelines of the *Consolidated Standards of Reporting Trials* (CONSORT; Boutron et al., 2017) and the SPIRIT guidelines (Chan et al., 2013).

Randomisation

We wish to recruit 60 clients who will be randomised for the modular patient-centred CBT (MPC) or a control treatment, where the order of the treatment modules is determined in advance (described in more detail below). A randomisation list will be prepared using R software (www.r-project.org). Participants will be randomised into an intervention group (MPC) or a control group (MPC without co-decision) with 30 participants in each group, stratified by recruitment/treatment site. A block size of six will be used to ensure an even balance. The randomisation list will be prepared by a data manager affiliated with the project, and only he will be able to see the randomisation list. First, the assessing psychologist will complete the informed consent procedure, and then the therapist will perform the 2nd measurement ('Beginning of treatment', see Table 2 below) with the client (by having the client complete a questionnaire package on a small laptop with

pressure sensitive screen (tablet). The random allocation will then take place automatically on the tablet if the therapist determines that the client meets the inclusion criteria.

Intervention: Modular Patient Centred CBT for CPTSD

MPC (Folke, Friis, Thomsen & Roitmann, 2020) is a treatment programme consisting of up to 32 therapy sessions broken down by five treatment modules (each consisting of six sessions). Prior to the treatment modules, the client will complete an intro module (two sessions) focusing on psychoeducation on CPTSD, individual case formulation and introduction to the further treatment programme (including the content of the different modules). After the intro module (and after each treatment module), the client and therapist jointly decide which treatment module to proceed with based on 'co-decision', which is described in more detail in the manual. The order of the treatment modules is decided on the basis of a joint assessment of the client's most prominent symptoms, the client's preferences and wishes as well as the client's state of readiness to work with e.g. trauma processing.

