Because the study investigates a potentially beneficial effect of including the client directly in treatment decisions (by having the client determine the order of treatment modules together with the therapist), the patient-centred version of the treatment is compared (as laid down in the treatment manual; Folke, Friis, Thomsen and Roitmann, 2020) with a control treatment, where the five treatment modules are delivered in a predefined order. The control treatment thus consists of the same treatment components as described above. It is only the aspect of co-decision that has been taken out. Instead, the therapist will just inform the client about the order of treatment modules in the programme. The order of treatment modules in the control treatment will be: 1) Affect dysregulation (6 sessions), 2) Disturbed relationships (6 sessions), 3) Negative self-concept (6

² The combined CBT-I and ERRT treatment manual and workbook were developed in 2019 by Pruiksma, K. E., Taylor, D. J., Davis, J., Dietrich, J. R., Peterson, A. L., Balliett, N., Goodie, J. L., Miller, K., Grieser, E., Friedlander, J., Hryshko-Mullen, A. S., Rowan, A., Wilkerson, A., Hall-Clark, B., & Fina, B., Hummel, V., Casady, T., Tyler, H.

sessions), 4) PTSD symptoms (6 sessions) and 5) Insomnia and trauma-related nightmares (6 sessions).

Treatment modality

The treatment is offered as individual treatment, except the module on disturbed relationships, where the client is encouraged in the first session to complete the module with, for example, a partner or another important person in their life.

Treatment completion

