As an integral part of the treatment, a short assessment is conducted after each treatment module by having the client complete the primary outcome measure, the International Trauma Questionnaire (ITQ; Cloitre et al., 2018), which is used as a measure for assessing ICD-11 PTSD and CPTSD. In practice, the client fills in the ITQ on a tablet in the beginning of the last session of each treatment module, after which the client and therapist receive an automatic response on the tablet, establishing whether the client (based on the ITQ) continues to meet the diagnostic criteria for PTSD or CPTSD. If the client has achieved sufficient symptom recovery and no longer meets the diagnostic criteria for CPTSD, the client is considered a treatment completer. However, the client and the therapist might decide to continue treatment until the client no longer meets the diagnostic criteria for PTSD. In this way, treatment can continue up till 32 therapy sessions but client and therapist can end the treatment earlier if the client has a valid assessment and falls out of CPTSD criteria.

After completing the MPC treatment, the client cannot receive psychological treatment at the Danish Veteran Centre, until a three-month follow-up of the treatment effect has been completed. However, after a three-month follow-up, the client is welcome to seek psychological treatment again at the Danish Veteran Centre. If deemed relevant, the client is offered help and support from the Counselling and Rehabilitation Department as well as from the Family Unit under the Danish Veteran Centre, independently of the MPC treatment programme. If a client is assessed to require psychological treatment before the three-month follow-up, this will be initiated. As part of the three-month follow-up, all clients respond to whether they have received other help and support from the Danish Veteran Centre or others after ending their MPC treatment.

Practical implementation

Treatment sites and participating therapists (will be updated regularly)

The treatment is carried out at five local veteran centres in Denmark by six clinical psychologists employed by the MPD, Danish Veteran Centre:

1. [name]. Clinical psychologists: [name] and [name].
2. [name]. Clinical psychologist: [name]
3. [name]. Clinical psychologist: [name]

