3. **2nd measurement ('Beginning of treatment') and randomisation.** During the initial interview, the treating psychologist provides oral information about the research project and hands over further written participant information and a consent form. The treating psychologist points out that the client has one week to decide whether S/he wishes to participate in the research project and that s/he can withdraw his/her consent at any time. The client is informed that s/he will be offered other relevant treatment by the MPD, if s/he does not wish to participate in the research project. If the client wishes to participate in the research project and the therapist assesses that, based on the initial interview, the client meets the inclusion criteria, the psychologist initiates the 2nd measurement ('Beginning of treatment'), involving a questionnaire package that the client is to fill in on a tablet. The questionnaires of the 2nd measurement are presented in Table 2 and are further described in the section 'Evaluation and Effect Analysis'. To complete the client's response to the 2nd measurement, the random allocation of the client for either intervention (MPC) or control treatment (MPC without co-decision) is automatically carried out on the tablet, as described in the 'Randomisation' section.
4. After that, either intervention (MPC) or control treatment (MPC without co-decision) is carried out as prescribed in the treatment manual.
5. **3rd measurement ('Continuous process and effect evaluation').** After each treatment module including the intro module (see detailed description of the MPC treatment programme below), a brief assessment is conducted. This includes four questionnaires as shown in Table 2. The client completes these questionnaires on the tablet, and the client and therapist automatically receive a response as to whether the client still suffers from C/PTSD, based on the ITQ (primary outcome measure). When the therapist and client decide to end the treatment, the therapist asks the client to complete the final questionnaires (4th measurement) on the tablet.
6. **4th measurement ('End of treatment').** At the end of treatment (see description below) the 4th measurement ('End of treatment') is completed on the tablet.
7. **5th measurement ('3-month follow-up').** Three months after completing the 'End of treatment' assessment, the client will receive a questionnaire package in their e-Boks as a three-month follow-up assessment.

Record keeping

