4. STATISTICAL CONSIDERATIONS

Number of subjects

Strength calculation is not required for pilot studies for Phase III trials and is in some cases even advised against (Billingham et al., 2013; Thabane et al., 2010). Based on comparable feasibility studies on testing new treatment methods for clients with PTSD (Mahoney et al., 2020; Scharff et al., 2020), we have estimated that 30 participants in the intervention and 30 in the control group are required for a representative sample.

Statistical analysis

Data from this pilot study will help provide information for a future efficacy RCT (Phase III trial) by testing the trial procedures. Therefore, no formal statistical analysis of data from the pilot study will be carried out. A description of the participants and a simple compiling of pilot data will be presented. Exploratory analyses will be conducted to compare means (and 95% confidence intervals) of the ITQ and the other secondary outcome measures between intervention and control group at the end of the treatment using a t-test. Furthermore, repeated measurements within the same group will be analysed using variance analysis (ANOVA). All randomised participants will be included in the analyses. The statistical analyses of pilot data will only be exploratory since the sample size does not allow for definitive analyses.

We will consider the study as complete if the following success criteria are met:

1. > 70% of potential participants accept and be included in the study

2. Completion rate of 70%, that is, we expect to have complete data (Measurement 4, completed at the final therapy session) of at least 70% of all participants included
3. Complete three-month follow-up (Measurement 5, obtained via e-Box) of at least 50% of all participants included

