12. RECRUITMENT OF PARTICIPANTS AND INFORMED CONSENT

All clients from the MPD contact the Danish Veteran Centre for treatment on their own initiative. When they contact the Danish Veteran Centre, they are invited to a visitation interview with a psychologist to assess whether their problems are deployment-related. If the assessing psychologist deems MPC to be a relevant offer for the client, the assessing psychologist informs the client of the research project. If the client expresses an interest in hearing more about the treatment and the research project, s/he is invited to an initial interview. The client is informed that they can bring a companion to the interview.

The initial interview takes place in a treatment room where only the treating psychologist, the potential participant and any companion are present. During this interview, oral information about the treatment and the research project is provided and further written participant information and a consent form are handed out. In the written material, the client can find contact information on the principal investigator and project manager, who can be contacted if the client requires further information about the project. The psychologist stresses that the client has a week to decide whether they wish to participate in the project and that their consent can be withdrawn at any time. The client is informed that they will receive other relevant treatment at the MPD, if they do not wish to participate in the pilot trial.

If the client wishes to participate in the pilot trial, further diagnostic investigation is initiated. If the inclusion criteria are met, randomisation is initiated for further treatment. If the client has a more severe diagnosis requiring treatment, in addition to CPTSD, the client will be offered other relevant treatment.

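### The protocol prints one fixed block size of six within sites, so a treating psychologist who knew it and tracked allocations in order could deduce some of them with certainty

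*Combined protocol and SAP*

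**What the plan says.** All references are to the combined protocol and SAP.

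- **Scheme.** Section 3, Randomisation, plans 60 clients "with 30 participants in each group, stratified by recruitment/treatment site", and adds: "A block size of six will be used to ensure an even balance". No other size is mentioned, so the natural reading is 3:3 blocks within each site.
- **Safeguards.** The same section has the list prepared by a data manager, who alone can see it. Allocation is automatic.
- **Last step before allocation.** "The random allocation will then take place automatically on the tablet if the therapist determines that the client meets the inclusion criteria". Step 3 of the Referral procedure repeats this: if the client wishes to take part and "the therapist assesses that, based on the initial interview, the client meets the inclusion criteria, the psychologist initiates the 2nd measurement".
- **Knowledge of past allocations.** The arms differ in whether the psychologist decides the module order jointly with the client. In the control arm: "Instead, the therapist will just inform the client about the order of treatment modules in the programme". The psychologist therefore knows the arm of every client they treat.
- **Sites.** "The treatment is carried out at five local veteran centres in Denmark by six clinical psychologists". The list, marked as regularly updated, shows two psychologists at the first site and one at each of the other four.
- **Use of the data.** Section 4 plans exploratory t-tests between arms at end of treatment. It also says: "Data from this pilot study will help provide information for a future efficacy RCT (Phase III trial) by testing the trial procedures".

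**The concern.** Keeping the list secret and allocating by tablet protect the list itself. They do not stop someone from working out the next allocation once three clients of one arm have been seen in a block of six. At a single-psychologist site the person who could do this is also the person who rules on eligibility just before allocation.

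If eligibility rulings were influenced by a deduced allocation, the arms could differ in who was admitted, and the exploratory between-arm comparisons (section 2, secondary objectives; section 4) would carry that difference. Steering by exclusion could also lower the first success criterion in section 4, which counts potential participants who accept and are included. Allocation is, moreover, one of the procedures the pilot exists to test.

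Room for discretion is limited. The ITQ is scored by rule (section 3, Primary outcome measure), veteran status is defined by policy (section 5), and deployment-relatedness is assessed at the earlier visitation interview (section 12). The documents do not say at which step the exclusion criteria are judged. What remains is the psychologist's ruling from the initial interview and a route in section 12 that is not among the criteria in section 5: "If the client has a more severe diagnosis requiring treatment, in addition to CPTSD, the client will be offered other relevant treatment".

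**Working it through.** The plan gives no predictability figure, so there is none to reproduce. Its 30 per group is consistent with 60/6 = 10 full blocks, provided every site ends on a multiple of six.

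**Inputs from section 3:** block size 6, ratio 1:1, 60 clients, five sites, six psychologists. **Assumed:** clients per site, which the documents do not give.

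**One block.** There are C(6,3) = 20 equally likely 3:3 sequences. An allocation is certain when one arm already has three clients in the block. By position 1 to 6 the probability of this is 0, 0, 0, 0.1, 0.4, 1.0. The sum is 1.5, and 1.5/6 = 25%.

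**One site of n clients.** Expected certain allocations e(n) = 1.5 × floor(n/6) + the sum of the first (n mod 6) position probabilities. So e(9) = 1.5, e(10) = 1.6, e(11) = 2.0, e(12) = 3.0, e(16) = 3.1, e(20) = 4.5, e(22) = 4.6, e(24) = 6.0. At 10 clients, the average caseload (60/6), the share is 1.6/10 = 16%.

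**Whole trial, all allocations at every site known.**
- 12 at each site: 5 × 3.0 = 15; 15/60 = 25.0%. This ceiling needs every site to end on a multiple of six.
- 24/9/9/9/9: (6.0 + 4 × 1.5)/60 = 20.0%.
- 20/10/10/10/10: (4.5 + 4 × 1.6)/60 = 18.2%.
- Lowest over five-site splits of 60 with at least 4 per site: 18.0%, for example 9/9/10/10/22, (1.5 + 1.5 + 1.6 + 1.6 + 4.6)/60.

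**Whole trial, first-site psychologists not sharing** (first site taken as 12 to 24 clients). If they do not know the block boundaries, the first site contributes 0. If they do, all three clients of the used-up arm must be their own. With clients split evenly at random between the two, that has probability (1/2)³ = 1/8.

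| Split | First site at 0 | First site at 1/8 |
|---|---|---|
| 12 × 5 | 12.0/60 = 20.0% | 12.375/60 = 20.6% |
| 16/11/11/11/11 | 8.0/60 = 13.3% | 8.3875/60 = 14.0% |
| 20/10/10/10/10 | 6.4/60 = 10.7% | 6.9625/60 = 11.6% |
| 24/9/9/9/9 | 6.0/60 = 10.0% | 6.75/60 = 11.3% |

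**Sizes 4, 6 and 8 in random order.** Simulated for a guesser who knows the set of sizes and updates after each allocation, for sites of 6 to 24 clients:
- *Certain allocations:* about 1-3%.
- *Best-guess success:* 64-68% with fixed six, 65-67% varied. At 10 clients it is 65.0% against 66.0%; at 12 clients, 68.3% against 66.4%.
- *Predictable with at least 75% probability:* this rises at every size run, from 24-32% to 33-41%. For fixed six, the position probabilities are 0, 0, 0.4, 0.1, 0.4, 1.0. At 10 clients that gives (1.9 + 0.5)/10 = 24%, against 37% varied. At 12 clients it gives 3.8/12 = 32%, against 40%.
- *Balance:* with 12 clients at each site, the chance of exactly 30:30 falls from 100% to about 35% (mean overall difference 1.8 clients, 95th percentile 4). At the four uneven splits run it is about the same either way: 27-32% fixed, 30-32% varied.
- *Sizes 4 and 6 alone* would leave about 6% certain.

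**The case against.** The strongest case is that the consequence is small and the usual remedy is weak. The design is a pilot with no formal analysis; the arms share all treatment components and differ only in co-decision; entry rests largely on rule-based criteria. Deduction requires knowledge that the documents do not say therapists have. Varying the block sizes does not reliably reduce guessing, since certain cases become probable ones, and it gives up the even balance for which six was chosen.

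Most of this stands. It makes varied blocks optional and keeps the point minor. It does not remove the mechanism: the size is printed, nothing says it is withheld, and past allocations are visible to the person ruling on eligibility.

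Some stronger readings are tempting but not supported:
- *That therapists know the block size.* The documents are silent.
- *That a quarter of allocations are predictable.* That needs full sharing at the first site and every site ending on a multiple of six.
- *That selection bias will occur.* Opportunity is not evidence, and discretion is limited.
- *That the future Phase III trial inherits the problem.* Nothing commits it to blocks of six.

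**Conclusion.** The point holds as a minor weakness in allocation concealment that is worth correcting. A psychologist who knew the block size, tracked allocations in order and knew the block boundaries could deduce about 10-21% of the trial's allocations if the first-site psychologists do not share, and 18-25% if all are known at every site. These are expected values at 60 clients under assumed site sizes, with the listed staffing of one psychologist at four sites.

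The exposure is to the exploratory between-arm comparisons and, if steering took the form of exclusion, to the uptake criterion. The completion and follow-up criteria are not directly at issue. A reader might infer that randomly varied blocks would cure the problem. They would remove nearly all certainty but not predictability.

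**What to change.** **Main change.** Remove the block size from section 3, Randomisation, and from every document the therapists see. State only that site-stratified permuted blocks are used and that the details are held by the data manager. Apply this to any list, or part of a list, not yet used; the documents do not give enrolment status. The cost is one or two sentences. It cannot undo knowledge that a therapist already has of a list in use.

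**Optional.** Generate the unused list with sizes 4, 6 and 8 in random order, keeping the set of sizes from therapists as well. If this is adopted, record the trade-off: certain allocations fall to about 1-3%, best-guess success is not consistently lower, the share predictable with at least 75% probability rises for someone who knows the set, and 30:30 is no longer assured when sites fill whole blocks. Section 3 names R but gives no script or tablet integration, so low effort is an assumption.

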The treatment is registered in COSMIC (the record keeping system used at the MPD). Treatment record is used for treatment sessions, and the treatment ends with a concluding record.

Supervision

The participating therapists receive method-specific supervision in MPC every 14 days by supervisors [name] and [name], who have been involved in the development of the treatment programme. In addition, all therapists receive supervision in Trauma-Focused Cognitive Behavioral Therapy on a monthly basis, as part of the regular routine at the MPD.

Evaluation of treatment effects

A thorough effect evaluation of the MPC treatment programme will be carried out with questionnaires completed by the clients before, during and after the treatment. In addition, the therapeutic process will be evaluated with questionnaires completed by the client after each treatment module.

Table 2 provides an overview of all measurement times and questionnaires used for the process and outcome assessment of the MPC treatment programme.

Questionnaires	Num- ber of items	Time of admin- istration (minutes)	Measurement times				
			Before treatment 1st measurement 'Baseline' (package of question- naire is sent to the cli- ent's e-Boks as part of the regular procedure at the MPD)	During treatment 2nd measurement 'Beginning of treat- ment' Questionnaire package is completed on tablet before randomisation and first therapy ses- sion	3rd measurement 'Continuous process and effect evaluation' ^a Four questionnaires are completed after each treat- ment module	After treatment 4th measurement 'End of treatment' Questionnaire package is completed on tablet after last therapy session	3-month follow-up 5th measurement '3-month follow-up' (questionnaire package is sent to the client's e-Boks)
Demographic in- formation	5	2:23	X			X	X
Suicidal thoughts and behaviour	4	0:35	X			X	X
Prior treatment	7	0:52	X				
Medicine	2	0:22				X	X
TLEQ	23	7:33	X			X	X
DASS-42	42	2:50	X			X	X
ITQ	20	2:49	X	X	X	X	X
PCL-C	17	1:49	X			X	X
ADRS	6	0:48	X				
Alcohol intake	3	1:02	X			X	X
Drugs	7	0:49	X			X	X
WHO-5	5	1:02	X	X		X	X
SDS	3	1:01	X	X		X	X
ACE	25	5:40		X			
ISI	7	1:40		X		X	X
CMDQ	12	2:58		X		X	X
ECR-S	12	2:24		X		X	X
Social support	12	2:20		X		X	X
Other help and support	10	2:00				X	X
CMTS	24	2:38			X		
SAI	6	0:44			X		

Number of items	142	106	57	237	184
Estimated use of time (minutes)	24	20	7	30	34

Table 2. Overview of measurement times and questionnaires

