Note: ^a Note that measurement 3 occurs after each treatment module (including the intro module) and is thus carried out several times (depending on the length of the client's course of treatment).

TLEQ = Traumatic Life Events Questionnaire; Dass-42 = Depression Anxiety Stress Scales; ITQ: International Trauma Questionnaire (primary outcome measure); PCL-C = Posttraumatic Stress Disorder Checklist - Civilian Version; ADRS = ADHD Symptom Checklist for Children - The Adult Self Report Symptoms of Childhood Scale; WHO-5 = WHO-Five Well-being Index; SDS = Sheehan Disability Scale; ACE = The Adverse Childhood Experiences questionnaire; ISI = The Insomnia Severity Index; CMDQ = item 1-12 from the Common Mental Disorders Questionnaire; ECR-S = The Experiences in Close Relationships - Short Form; CMTS: Client Motivation for Therapy Scale; SAI = Session Alliance Inventory

Measures

See Table 2 for an overview of measurement times.

Demographic information. Five questions examine the client's gender, age, marital status, job position and children.

Suicidal thoughts and behaviour are assessed with four questions regarding suicidal thoughts, plans and previous suicide attempts. Two questions are to be answered on a 5-point scale from 'Never' to 'Very Often', examining suicidal thoughts and plans in the last six months. Two others are to be answered with 'Yes/No', examining suicide attempts in the last year and before that. The four questions have been used in EPSIS, the WHO study ('Euro Multicentre Study of Suicidal Behavior') as well as national surveys (SuSY, the National Institute of Public Health, University of Southern Denmark) and in studies by the Danish Centre for Suicide Research.

Previous treatment and medication. Previous treatment is assessed with five questions that examine whether the client has received treatment in the past due to psychological or psychiatric problems, whether the client has been diagnosed and whether the client is still in treatment. Medication is assessed with two questions, asking whether the client has received any prescription or nonprescription medicines in the last 14 days, and if so, what the medicine is called.

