6. RISKS, SIDE EFFECTS AND SHORT- AND LONG-TERM DISADVANTAGES

No side effects are expected in the short or long term by participating in the psychotherapeutic MPC treatment programme, and no known side effects of similar psychotherapeutic interventions are described in the literature. In the case of side effects that do not go away within 1-2 therapy

³ According to the Veteran Policy of Denmark of 5 September 2016, a veteran is defined as 'a person who has been deployed in international operations at least once, on the grounds of a decision made by Folketinget, the Danish Government or a minister' regardless of whether they still serve in the military (<https://fmn.dk/temaer/veteraner/Documents/the-veteran-policy-of-denmark-2016.pdf>)

⁴ To a degree that will make it difficult to complete the manualised treatment programme

⁵ E.g. if the client shows up under the influence of intoxicants

⁶ For example, the client cannot simultaneously participate in other research projects in the Danish Veteran Centre, such as evaluation of body therapy with BBAT for PTSD.

sessions, the client will be offered other relevant treatment at the MPD. Any side effects are registered by the therapist. The client may always withdraw from the MPC treatment if they do not wish to continue, and the client is informed that this will not affect their possibilities of receiving other relevant psychological treatment at the MPD.

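### The one-year suicide-attempt question, repeated at end of treatment and at follow-up, cannot date a repeat Yes to the treatment or follow-up period

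*Combined protocol and SAP*

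**What the plan says.** Under Measures in Section 3, four questions cover suicidality. Two are five-point frequency ratings "examining suicidal thoughts and plans in the last six months". Two are Yes/No items "examining suicide attempts in the last year and before that". In Table 2 the row "Suicidal thoughts and behaviour" is marked at Measurements 1, 4 and 5. No version with a different time reference is described for the later measurements.

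Course length varies. The part headed Treatment completion sets a ceiling of 32 sessions. It also allows an earlier stop: "client and therapist can end the treatment earlier if the client has a valid assessment and falls out of CPTSD criteria". The follow-up package is sent "Three months after completing the 'End of treatment' assessment" (Referral procedure, step 7). Neither the session frequency nor the calendar length of treatment is given.

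On harms, Section 6 says "No side effects are expected in the short or long term" and adds "Any side effects are registered by the therapist", with no form or definition. Section 8 says that patient records will not be used.

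**The concern.** A question repeated after treatment tells the reader about treatment only if its time reference can be lined up with the treatment period. Here the reference is fixed at six months or one year, while treatment length varies and follow-up lasts three months. An attempt already reported at baseline can properly be reported again at Measurement 4, and one reported at Measurement 4 can be reported again at Measurement 5.

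The clients most affected are those whose events matter most. Section 5 excludes only clients whose suicidality would make the programme hard to complete, so clients with lesser ideation or past attempts can enter. With records unavailable, these items are the only structured data on suicidal thoughts and attempts. Assessing data collection is a primary objective of this pilot, so this is the stage at which to correct the wording.

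**Working it through.** **Inputs**

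- Recall windows (Measures): six months = 26 weeks; one year = 52 weeks.
- Measurement 4 to Measurement 5 (Referral procedure): three months = 13 weeks.
- Sessions: 2 introductory + 5 × 6 = 32, which reproduces the plan's maximum. Status is checked in the last session of each module, so planned ends fall at 8, 14, 20, 26 or 32 sessions.
- Weeks per session: not stated. Assumed 1, with a range of 0.5 to 2.
- Timing of the items: the marked rows of Table 2, including the four suicidality items, add to 142 at Measurement 1 and 184 at Measurement 5, as printed. At Measurements 2, 3 and 4 they add to 96, 50 and 184 against printed totals of 106, 57 and 237, so some marks may be missing from the text read here. The suicidality mark at Measurement 4 is visible. Its absence at Measurement 2 is read from the visible marks only.

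**Step 1: what holds at any pace.** At Measurement 5 the one-year window covers 52 − 13 = 39 weeks before Measurement 4. The six-month window covers 26 − 13 = 13 weeks before it.

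**Step 2: reach before treatment, weekly sessions assumed.** Let T = sessions × weeks per session and W = window. Pre-treatment weeks inside the window are max(0, W − T) at Measurement 4 and max(0, W − 13 − T) at Measurement 5.

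| Sessions (T in weeks) | One-year, M4 | One-year, M5 | Six-month, M4 | Six-month, M5 |
|---|---|---|---|---|
| 8 | 44 | 31 | 18 | 5 |
| 14 | 38 | 25 | 12 | 0 |
| 20 | 32 | 19 | 6 | 0 |
| 26 | 26 | 13 | 0 | 0 |
| 32 | 20 | 7 | 0 | 0 |

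**Step 3: other paces.**

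- Two sessions a week, 32 sessions (T = 16): one-year 36 and 23 weeks; six-month 10 and 0.
- One session every two weeks, one-year item at M4 and M5: 8 sessions (T = 16) gives 36 and 23; 14 sessions (T = 28) gives 24 and 11; 20 sessions (T = 40) gives 12 and 0; 26 sessions (T = 52) and 32 sessions (T = 64) give 0 and 0.
- General rule: the one-year item reaches before treatment if T is under 52 weeks at Measurement 4 or under 39 weeks at Measurement 5. For the six-month items the limits are 26 and 13 weeks.
- A slow pace produces the opposite mismatch. At T = 64 the one-year window at Measurement 4 misses the first 64 − 52 = 12 weeks of treatment.

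These weeks are counted back from the start of treatment. Part of them lies between Measurement 1 and that start, an interval the protocol does not give, so the reach before Measurement 1 is shorter by that interval.

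**Step 4: what the answer patterns show** (assuming consistent recall).

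- No to both attempt items at Measurement 1, Yes later: a new attempt since Measurement 1. With no visible repeat at Measurement 2, it cannot be placed before or after randomisation.
- No to the last-year item at Measurement 1, Yes to it at Measurement 4: also since Measurement 1, because the later window opens later. In the same way, No at Measurement 4 and Yes at Measurement 5 points to follow-up.
- Yes to the last-year item at Measurements 1 and 4: possibly the same event whenever the two are under 52 weeks apart.
- Yes to it at Measurements 4 and 5: possibly the same event at any pace, since 13 < 52.
- A repeat Yes to the item on earlier attempts adds nothing.

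**The case against.** The case for leaving the items alone is substantial. The baseline answers already separate new from old for most clients, as Step 4 shows. The pre-treatment overlap depends on a pace that the protocol does not state, and a full course at one session every two weeks has none. Suicidality is neither an objective nor a listed secondary outcome, and no arm comparison of it is planned. Better wording would not make one informative: at the 70% completion target each arm has 0.70 × 30 = 21 clients, and zero attempts among 21 still leaves a one-sided 95% upper bound of 1 − 0.05^(1/21), about 13%. Therapists register side effects, and worsening can be seen on the ITQ after each module and on the DASS-42 and PCL-C at Measurements 4 and 5. The wording has been used in earlier surveys. Re-anchoring the frequency ratings would lose change from baseline.

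All of this stands, and it limits the point. The thoughts and plans ratings should keep their wording, and the point concerns description of safety rather than inference. It does not remove the 39 weeks of Step 1 or make a repeat Yes datable. Therapist registration, with no definition or form, is not an assured substitute.

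**Conclusion.** The point holds for the attempt item. At any pace, a Yes at both Measurements 4 and 5 cannot be assigned to follow-up. A Yes to the last-year item at both Measurements 1 and 4 cannot be identified as new when they are less than a year apart. On the weekly assumption, the last-year item includes 20 to 44 pre-treatment weeks at Measurement 4 and 7 to 31 at Measurement 5. The six-month ratings can also mix periods, but reach before treatment only for courses under 26 weeks at Measurement 4 or under 13 weeks at Measurement 5.

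A reader might infer that the trial cannot tell new events from old at all, that every window reaches before treatment for every client, or that no other harm data exist. The documents support none of these: baseline carries the same items, the overlap varies with an unstated duration, and side effects are also registered. Nor is the statement that no side effects are expected a hypothesis the pilot sets out to test. This is an inexpensive refinement of descriptive safety data and does not affect the feasibility conclusions.

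**What to change.** Keep all four items as worded at Measurement 1, and keep the two six-month ratings unchanged throughout. At Measurement 4 ask the last-year attempt item for the time since treatment began. At Measurement 5 ask it for the time since the end-of-treatment questionnaire. The companion item on earlier attempts can stay and would then refer to the time before the new period. Report the number of clients with an attempt by arm and period, together with the length of each period, and state that this is descriptive and not a formal comparison.

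The cost is a changed time stem on the tablet and e-Boks forms, with no added items. The later attempt answers will no longer match the original survey wording. The period covered at Measurement 4 will vary with treatment length, which may itself differ between arms because ending early depends on response; that is why the period lengths must be shown beside the counts. The re-anchored item will not cover the interval between Measurement 1 and the start of treatment.
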